3. PRIMARY AND SECONDARY VARIABLES

At each visit patients will be assigned a RECIST visit response of complete response (CR), partial response (PR), stable disease (SD), progressive disease (PD), not evaluable (NE) or NED depending on the status of their disease compared to baseline and previous assessments, based on the BICR. This will be repeated using the Investigator assessed RECIST data.

3.1 Derivation of RECIST Visit Responses

Patients with measurable or non-measurable disease or NED assessed at baseline by computed tomography (CT) / magnetic resonance imaging (MRI) will be entered in this study. RECIST has been modified to allow the assessment of progression due to new lesions in patients with NED at baseline (inclusion criteria #4).

For all patients, the RECIST tumour response data will be used to determine each patient's visit response according to modified RECIST version 1.1. It will also be used to determine if and when a patient has progressed in accordance with RECIST and also their best overall response.

Baseline radiological tumour assessments are to be performed no more than 28 days before start of study treatment and ideally as close as possible to the start of study treatment and prior to randomisation. Tumour assessments are then performed every 8 weeks (± 1 week) up to 40 weeks and then every 12 weeks (± 1 week) following randomisation until disease progression.

If an unscheduled assessment was performed and the patient had not progressed, every attempt should be made to perform the subsequent assessments at their scheduled visits. This schedule is to be followed in order to minimise any unintentional bias caused by some patients being assessed at a different frequency than other patients.

At each visit, an overall visit response will be provided by the BICR and separately by the investigator - using the information from target lesions (TL), non-target lesions (NTL) and new lesions.

3.1.1 Target lesions

Measurable disease is defined as having at least one measurable lesion, not previously irradiated, which is ≥ 10 mm in the longest diameter (except lymph nodes which must have

short axis ≥ 15 mm) with CT or MRI and which is suitable for accurate repeated measurements.

A patient can have a maximum of 5 measurable lesions recorded at baseline with a maximum of 2 lesions per organ (representative of all lesions involved suitable for accurate repeated measurement) and these are referred to as TLs. If more than one baseline scan is recorded, then measurements from the one that is closest to and prior to randomisation will be used to define the baseline sum of TLs. It may be the case that, on occasion, the largest lesion does not lend itself to reproducible measurement in which circumstance the next largest lesion, which can be measured reproducibly, should be selected.

All other lesions (or sites of disease) not recorded as TLs should be identified as NTLs at baseline. Measurements are not required for these lesions, but their status should be followed at subsequent visits.

Note: For patients who do not have measurable disease at entry (ie, no TLs) but have non-measurable disease, evaluation of overall visit responses will be based on the overall NTLs assessment and the absence/presence of new lesions (see [Section 3.1.3](#) of the Clinical Study Protocol (CSP) for further details). If a patient does not have measurable disease at baseline, then the TL visit response will be not applicable (NA).

For patients with NED at baseline (ie, no TLs and no NTLs), evaluation of overall visit responses will be based on absence/presence of new lesions. If no TLs and no NTLs are recorded at a visit, both the TL and NTL visit response will be recorded as NA and the overall visit response will be NED.

Table 3 TL Visit Responses

Visit Responses	Description
CR	Disappearance of all TLs since baseline. Any pathological lymph nodes selected as TLs must have a reduction in short axis to <10 mm.
PR	At least a 30% decrease in the sum of diameters of TLs, taking as reference the baseline sum of diameters.
SD	Neither sufficient shrinkage to qualify for PR nor sufficient increase to qualify for PD.
PD	At least a 20% increase in the sum of diameters of TLs, taking as reference the smallest sum on study (this includes the baseline sum if that is the smallest on study). In addition to the relative increase of 20%, the sum must also indicate an absolute increase of at least 5 mm.
NE	Only relevant if any of the TLs were not assessed or not evaluable or had a lesion intervention at this visit. Note: If the sum of diameters meets the PD criteria, PD overrides NE as a TL response.
NA	No TLs are recorded at baseline.

Rounding of TL data

For calculation of PD and PR for TLs, percentage changes from baseline and previous minimum should be rounded to 1 decimal place before assigning a TL response. For example 19.95% should be rounded to 20.0% but 19.94% should be rounded to 19.9%.

Missing TL data

For a visit to be evaluable, all TL measurements should be recorded. However, a visit response of PD should still be assigned if any of the following occurred:

- A new lesion is recorded.
- A NTL visit response of PD is recorded.
- The sum of TLs is sufficiently increased to result in a 20% increase, and an absolute increase of ≥ 5 mm from nadir, even assuming the non-recorded TLs have disappeared. Note: the nadir can only be taken from assessments where all the TLs had a longest diameter (LD) recorded, including non-missing TLs which have had intervention during the study and prior to any scaling of the measurements.

If there is at least one TL measurement missing and a visit response of PD cannot be assigned, the visit response is NE.

Lymph nodes

For lymph nodes, if the size reduces to < 10 mm then these are considered non-pathological. However, a size will still be given, and this size should still be used to determine the TL visit response as normal. In the special case where all lymph nodes are < 10 mm and all other TLs are 0 mm, then although the sum may be > 0 mm the calculation of TL response should be over-written as a CR.

TL visit responses subsequent to CR

A CR can only be followed by CR, PD or NE. If a CR has occurred then the following rules at the subsequent visits must be applied:

- Step 1: If all lesions meet the CR criteria (ie, 0 mm or < 10 mm for lymph nodes) then response will be set to CR irrespective of whether the criteria for PD of TL is also met ie, if a lymph node LD increases by 20% but remains < 10 mm.
- Step 2: If some lesion measurements are missing but all other lesions meet the CR criteria (ie, 0 mm or < 10 mm for lymph nodes), then response will be set to NE irrespective of whether when referencing the sum of TL diameters the criteria for PD is also met.

- Step 3: If not all lesions meet the CR criteria and the sum of lesions meets the criteria for PD, then response will be set to PD.
- Step 4: If after steps 1 – 3 a response can still not be determined, the response will be set to remain as CR.

TL too big to measure

If a TL becomes too big to measure, this should be indicated in the database and a size ('x') above which it cannot be accurately measured should be recorded. If using a value of x in the calculation of TL response would not give an overall visit response of PD, then this will be flagged and reviewed by the study team blinded to treatment assignment. It is expected that a visit response of PD will remain in the vast majority of cases.

TL too small to measure

If a TL becomes too small to measure a value of 5 mm will be entered into the database and used in TL calculations, unless the radiologist has indicated and entered a smaller value that can be reliably measured. If a TL response of PD results, then this will be reviewed by the study team blinded to treatment assignment.

Irradiated lesions/lesion intervention

Previously irradiated lesions (ie, lesion irradiated prior to entry into the study) should be recorded as NTLs and should not form part of the TL assessment.

Any TL (including lymph nodes), which has had intervention during the study (for example, irradiation / palliative surgery / embolization), should be handled in the following way and once a lesion has had intervention then it should be treated as having had intervention for the remainder of the study, noting that an intervention will most likely shrink the size of tumours:

- Step 1: the diameters of the TLs (including the lesions that have had intervention) will be summed and the calculation will be performed in the usual manner. If the visit response is PD this will remain as a valid response category.
- Step 2: If there was no evidence of progression after step 1, treat the lesion diameter (for those lesions with intervention) as missing and if $\leq 1/3$ of the TLs have missing measurements, then scale up as described below. If the scaling results in a visit response of PD then the patient would be assigned a TL response of PD.

Scaling will be based on the measurements at the nadir visit, to give an estimated sum of diameters and this will be used in calculations; this is equivalent to comparing the visit sum of diameters of the non-intervention lesions to the nadir sum of diameters excluding the lesions with interventions.

Table 4 Example of scaling

Lesion	Longest diameter at nadir visit	Longest diameter at follow-up visit
1	7.2	7.1
2	6.7	6.4
3	4.3	4.0
4	8.6	8.5
5	2.5	Intervention
Sum	29.3	26

Lesion 5 has had an intervention at the follow-up visit.

The sum of lesions 1 to 4 at the follow-up is 26 cm. The sum of the corresponding lesions at baseline visit is 26.8 cm.

Scale up as follows to give an estimated TL sum of 28.4 cm:

$$\frac{26}{26.8} \times 29.3 = 28.4 \text{ cm}$$

- Step 3: If after both steps PD has not been assigned, then if appropriate, a scaled sum of diameters will be calculated (as long as $\leq 1/3$ of the TLs have missing measurements), treating the lesion with intervention as missing, and PR or SD, then assigned as the visit response. Patients with intervention are evaluable for CR as long as all non-intervened lesions are 0 (or < 10 mm for lymph nodes) and the lesions that have been subject to intervention also have a value of 0 recorded. If scaling-up is not appropriate due to too few non-missing measurements then the visit response will be set as NE.

At subsequent visits the above steps will be repeated to determine the TL and overall visit response. When calculating the previous minimum, lesions with intervention should be treated as missing and scaled up where appropriate (as per step 2 above).

Lesions that split in two

If a TL splits in two, then the LDs of the split lesions should be summed and reported as the LD for the lesion that split.

Lesions that merge

If two TLs merge, then the LD of the merged lesion should be recorded for one of the TL sizes and the other TL size should be recorded as 0 mm.

Change in method of assessment of TLs

Computed tomography (CT) and MRI are the only methods of assessment that can be used within the trial. If a change in method of assessment occurs between CT and MRI, this will be considered acceptable and no adjustment within the programming is needed.

If a change in method involves clinical examination (eg, CT changes to clinical examination), any affected lesions should be treated as missing.

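### After a target-lesion CR, step 4 of SAP 3.1.1 scores a visit with a missing lesion and regrowth below PD as CR, while the missing-data rule in the same section scores it NE

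*SAP*

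**What the plan says.** All the rules at issue stand in SAP 3.1.1.

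The paragraph on missing TL data sets the general rule: "If there is at least one TL measurement missing and a visit response of PD cannot be assigned, the visit response is NE". When PD is tested with a TL unmeasured, that TL is counted as having vanished.

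The paragraph on responses after a CR limits the outcomes ("A CR can only be followed by CR, PD or NE") and makes its steps mandatory: "If a CR has occurred then the following rules at the subsequent visits must be applied".

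- Step 1 keeps CR when every lesion meets the CR criterion (0 mm, or under 10 mm for a node).
- Step 2 opens "Step 2: If some lesion measurements are missing but all other lesions meet the CR criteria" and continues: "then response will be set to NE irrespective of whether when referencing the sum of TL diameters the criteria for PD is also met".
- Under step 3, PD is assigned when a lesion no longer meets CR and the recorded sum reaches the PD threshold.
- Last, step 4 takes everything else: "Step 4: If after steps 1 – 3 a response can still not be determined, the response will be set to remain as CR".

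Table 3 defines target-lesion PD as an increase over the smallest sum on study of at least 20% and at least 5 mm. SAP 3.2 has the investigator overall visit response derived by program from the site's lesion data. SAP 3.1.4 has the BICR define its own overall visit responses.

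**The concern.** Step 2 catches a missing measurement only while every measured lesion still meets CR. Once a measured lesion stops meeting CR, the visit leaves step 2. If the growth is too small for step 3, it falls to step 4 and is scored CR. As the measured lesion grows, the result runs NE, then CR, then PD, so a visit with worse data scores better than one with no regrowth. The general rule, a few lines earlier, gives NE for the middle case. The section therefore gives two answers for one visit and does not say which prevails.

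The stake is evaluability. Under Table 6, a TL response of CR yields an overall CR or PR, and a TL response of NE yields NE, provided there is no non-target progression and no new lesion. Under SAP 3.2.1, the last evaluable assessment fixes the PFS censoring date and starts the count for the missed-visit rule.

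**Working it through.** This is decision logic, so the plan has no figure to reproduce. The inputs are steps 1 to 4, the Table 3 PD thresholds, and the rule that an unmeasured TL counts as 0 mm when PD is tested. Where the nadir is 0 mm, any increase is taken to satisfy the 20% condition.

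**Which response the steps give.** PD needs a recorded sum of at least nadir × 1.2 and at least nadir + 5 mm. One TL is missing in every row.

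| State at CR | Nadir | PD from | Steps 2, 4, 3 by size of the measured lesion | General rule where step 4 gives CR |
|---|---|---|---|---|
| Node 8 mm, non-nodal lesion 0 mm (missing) | 8 | max(9.6, 13) = 13 mm | up to 9.9: NE; 10 to 12.9: CR; 13 or more: PD | NE |
| Two non-nodal lesions at 0 mm, one missing | 0 | 5 mm | 0: NE; above 0 and below 5: CR; 5 or more: PD | NE |
| Two nodes of 9 mm, one missing | 18 | max(21.6, 23) = 23 mm | up to 9.9: NE; 10 to 22.9: CR; 23 or more: PD | NE |

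The third row is wide because the missing node counts as 0 mm against a nadir that includes it. The second is narrow: a lesion too small to measure is entered as 5 mm by default, which already meets Table 3 from a nadir of 0 mm.

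SAP 3.2.1 words the absolute increase as more than 5 mm, where Table 3 has at least 5 mm. That moves only the exact boundary (for example 13 mm in the first row) and does not alter the pattern.

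**What CR instead of NE does downstream.** Take a TL CR at week 16 and the disputed visit at week 24. SAP 3.2.1 treats a gap of more than 18 weeks as two missed visits in the first 40 weeks.

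| What follows week 24 | Week 24 = NE | Week 24 = CR |
|---|---|---|
| No later evaluable visit, alive, no PD | censored week 16 | censored week 24 (8 weeks later) |
| Week 32 evaluable, no PD | week 32 or later | same |
| PD at week 32 | gap 32 − 16 = 16 weeks: event week 32 | same |
| Week 32 missed, PD at week 40 | gap 40 − 16 = 24 weeks: censored week 16 | gap 40 − 24 = 16 weeks: event week 40 |

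After week 40 visits are 12 weeks apart, so the shift in the first pattern would be 12 weeks. The direction is not uniform: in the first pattern a censored time is lengthened, in the last a censored patient becomes an event.

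**Which analyses use it.**

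- Investigator PFS: the ascertainment-bias analysis at DCO1 (4.2.2.1) and the descriptive analysis at DCO2 (4.2.2, Table 10).
- PFS2, where SAP 3.2.3 applies the PFS censoring rules to patients without a first progression.
- Investigator duration of response, which SAP 3.2.8 ties to the PFS event or censoring date and Table 10 lists at DCO1 only.

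Investigator ORR is untouched: by Table 6 the earlier TL CR, without progression, has already given an overall CR or PR.

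**The case against.** The best reply is that the plan already contains the right answer. The missing-data paragraph is stated without exception, Table 3 links NE to lesions not assessed, and NE is an allowed outcome after a CR. On that reading, step 2 exists only to stop a PD call when all measured lesions still meet CR (a node going from 3 to 9 mm with another TL missing). The general rule handles missing-plus-regrowth, and step 4 is left for complete visits. This reading is workable, but the text does not compel it. Step 4 depends only on steps 1 to 3, and the steps are mandatory. Step 2 itself overrides the general rule, since it gives NE even where PD is met. A programmer could reasonably treat the post-CR block as controlling, and two programmers could code the same visit differently.

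Two stronger readings should be resisted, and here the other side is right.

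- A reader might infer that every triggered case moves the censoring date by 8 or 12 weeks. It does not: any later evaluable visit, or PD at the next visit, leaves the outcome unchanged.
- A reader might infer that the primary PFS is affected. The documents do not show this. The BICR defines its own visit responses, with details left to a charter that is not at hand, and primary PFS uses those responses.

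**Conclusion.** The contradiction is real: read literally, a mandatory rule returns CR for a visit that the same section calls NE, and no precedence is stated. It is minor. It reaches only the programmed investigator response and what draws on it. The censoring date changes only if the disputed visit would be the last evaluable one before censoring. Event status changes only if that visit adjoins another missed or unevaluable visit before progression or death.

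The documents give no frequency for target-lesion CR. If it were 2% to 4% of about 145 patients, that is 145 × 0.02 = 2.9 to 145 × 0.04 = 5.8, or about 3 to 6 patients. Each would also need an incomplete visit with regrowth inside the window below PD. None or one case is the realistic expectation. This is an assumption, not a figure from the plan.

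**What to change.** Reword step 4 along these lines: where steps 1 to 3 leave the response open, assign NE if any target-lesion measurement is missing (as the missing-data paragraph requires), and otherwise keep CR. Add that lesions with an intervention during the study continue to follow the intervention and scaling rules of SAP 3.1.1, so that treating them as missing for scaling does not by itself trigger NE here.

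Steps 1 to 3 stay as they are. After the change the three rows in the working run NE, NE, PD, and step 4 keeps CR only when all target lesions were measured.

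The cost is one sentence in the SAP and one condition in the response program. Because the study was unblinded for the DCO1 analysis, the change should be dated and justified. Any visit whose investigator response changes should be listed with its effect on PFS, PFS2 and duration of response. An empty list would close the point.

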3.1.2 NTLs and new lesions

At each visit an overall assessment of the NTL response should be recorded. This section provides the definitions of the criteria used to determine and record overall response for NTL at each visit.

The NTL response will be derived based on the overall assessment of NTLs as follows:

Table 5 NTL Visit Responses

Visit Responses	Description
CR	Disappearance of all NTLs present at baseline with all lymph nodes non-pathological in size (<10 mm short axis).
PD	Unequivocal progression of existing NTLs. Unequivocal progression may be due to an important progression in one lesion only or in several lesions. In all cases the progression MUST be clinically significant for the physician to consider changing (or stopping) therapy.
Non-CR/Non-PD	Persistence of one or more NTLs with no evidence of progression.
NE	Only relevant when one or some of the NTLs were not assessed and, in the investigator's opinion, they are not able to provide an evaluable overall NTL assessment at this visit. Note: For patients without TLs at baseline, this is relevant if any of the NTLs were not assessed at this visit and the progression criteria have not been met.
NA	Only relevant if there are no NTLs at baseline.

To achieve 'unequivocal progression' on the basis of NTLs, there must be an overall level of substantial worsening in non-target disease such that, even in presence of SD or PR in TLs, the overall tumour burden has increased sufficiently to merit discontinuation of therapy. A modest 'increase' in the size of one or more NTLs is usually not sufficient to qualify for unequivocal progression status.

The finding of a new lesion should be unequivocal: ie, not attributable to differences in scanning technique, change in imaging modality or findings thought to represent something other than tumour.

New lesions will be identified on the electronic case report form (eCRF). The absence and presence of new lesions at each visit should be listed alongside the TL and NTL visit responses.

A new lesion indicates progression so the overall visit response will be PD irrespective of the TL and NTL response.

A lesion identified at a follow-up assessment in an anatomical location that was not scanned at baseline is considered a new lesion and will indicate disease progression.

If the question ‘Any new lesions since baseline’ has not been answered with Yes or No and the new lesion details are blank this is not evidence that no new lesions are present and should be treated as NE in the derivation of overall visit response.

‘Symptomatic deterioration’ is not a descriptor for progression of NTLs: it is a reason for stopping study therapy and will not be included in any assessment of NTLs. Patients with symptomatic deterioration requiring discontinuation of treatment without objective evidence of disease progression at that time should continue to undergo tumour assessments where possible until objective disease progression is observed.

3.1.3 Overall visit response

Table 6 defines how the previously defined TL and NTL visit responses will be combined with new lesion information to give an overall visit response.

Table 6 Overall Visit Responses

Target lesions	Non-target lesions	New lesions	Overall response
CR	CR or NA	No (or NE)	CR
NA	CR	No (or NE)	CR
CR	Non-CR/Non-PD or NE	No (or NE)	PR
PR	Non-PD or NE or NA	No (or NE)	PR
SD	Non-PD or NE or NA	No (or NE)	SD
NA	Non-CR/Non-PD	No (or NE)	SD
NE	Non-PD or NE or NA	No (or NE)	NE
NA	NE	No (or NE)	NE
PD	Any	Any	PD
Any	PD	Any	PD
Any	Any	Yes	PD
NA	NA	No (or NE)	NED

NA is only relevant if there were no TL/NTL at baseline.

3.1.4 Independent review

A planned BICR of all radiological imaging data will be carried out using modified RECIST version 1.1 and these data will be used for the interim and primary analyses of PFS. All radiological scans for all patients (including those at unscheduled visits, or outside visit windows) will be collected on an ongoing basis and sent to an AstraZeneca appointed Contract Research Organisation (PAREXEL Imaging) for central analysis. Prior radiotherapy and location of screening biopsy lesion reports will also be provided to the BICR to allow the selection of appropriate TLs. The imaging scans will be reviewed by 2 independent radiologists using modified RECIST 1.1 and will be adjudicated, if required. For each patient, the BICR will define the overall visit response (ie, the response obtained overall at each visit by assessing TLs, NTLs and new lesions) data (for patients with TLs at baseline: CR, PR, SD, PD, NE; for patients with NTLs only: CR, SD, PD or NE; for patients with no disease identified at baseline: PD, NED, NE). If a patient has had a tumour assessment that cannot be evaluated then the patient will be assigned a visit response of NE (unless there is evidence of progression in which case the response will be assigned as PD).

RECIST assessments/scans contributing towards a particular visit may be performed on different dates and for the central review the date of progression will be determined based on the earliest of the scan dates of the component that triggered the progression, either for the adjudicated reviewer selecting PD or of the first reviewer where both select PD as time-point response and there is no adjudication.

Results of this independent review will not be communicated to Investigators and the management of patients will be based solely upon the results of the modified RECIST 1.1 assessment conducted by the Investigator.

On an ongoing basis, patients who are determined to have progressed according to modified RECIST 1.1 criteria by the investigator will have scans centrally reviewed for confirmation of objective disease progression. Radiological scans will only be sent for BICR up until the date of RECIST progression determined by the investigator. However, if disease progression is not confirmed at BICR, an additional RECIST assessment will be requested at the next scheduled RECIST visit. After the final PFS analysis, BICR of scans will no longer be required, regardless of progression status.

Further details of the BICR will be documented in the BICR Charter.

